9 STUDY MATERIALS

9.1 INVESTIGATIONAL STUDY PRODUCT

9.1.1 Description and Formulation

The active drug substance, idronoxil, is manufactured by chemical synthesis and is produced as a single monomer. Idronoxil is manufactured to > 98% purity.

Nomenclature

Codename: Idronoxil

Chemical Name: 2H-1-Benzopyran-7-O,1,3-(4-hydroxyphenyl)

Other names: Dehydroequol

Empirical Formula: C₁₅H₁₂O₃

Molecular Weight: 240.26 g/mol

NOX66 is idronoxil in a suppository dosage form for rectal delivery. The drug substance, idronoxil, is formulated in hydrogenated lipophilic base to yield suppositories with an approximate weight of 2.2 g and containing 400 mg drug substance.

9.1.2 Presentation, Storage and Handling

Presentation: NOX66 is presented as a solid dosage form as a suppository for rectal delivery.

NOX66 is presented in plastic sleeves in boxes. Each box contains 16 suppositories. Patients will be provided with 1, 2 or 3 boxes, depending on which cohort they are enrolled into.

NOX66 investigational product will be provided directly by the Sponsor to the clinical trials centres.

Storage and Handling: NOX66 boxes should be stored at the study centre in a secure area with limited access at 2-8°C (refrigerated) and protected from light. Any breach of investigational product storage conditions should be notified to the Sponsor on detection and the medication should be quarantined until the Sponsor authorizes usage or otherwise.

NOX66 is not expected to pose any safety risks to the Investigational staff under normal conditions of storage and distribution. Idronoxil has the lowest grade (Grade 4) of hazard classification (according to Regulation (EC) No. 1272/2008 [EU-GHS/CLP] with an acute oral

toxicity of between 300 to >2000 mg/kg body weight. The product also is contained within air-tight plastic moulding.

9.1.3 Labelling

Each box will be labelled with:

- the name of the Sponsor and address;
- the study protocol number;
- pharmaceutical dosage form, quantity of dosage units;
- name and strength of the product;
- the batch/lot number of the contents;
- period of use (expiry date or re-test date as applicable) in month/year;
- Caution Statement: "Caution: Clinical Trial Use Only; Keep out of reach of children.";
- storage instructions;
- PI name;
- Patient ID.

Each suppository will be labelled with:

- the name of Sponsor;
- the study protocol number;
- pharmaceutical dosage form, quantity of dosage units;
- name and strength of the product;
- the batch/lot number of the contents.

Boxes (plus any remaining contents) are to be accounted for.

9.1.4 Procurement and Distribution

NOX66 investigational product will be provided directly by the Sponsor.

Patients are to be given their NOX66 treatment following confirmation of eligibility (screening) and the scheduled commencement of treatment.

Patients to return medication following completion of NOX66 therapy for drug accountability.

9.2 INVESTIGATIONAL PRODUCT ADMINISTRATION

Idronoxil in the form of a suppository (NOX66) will be self-administered once, twice or three times daily depending on the patient cohort allocation and continue for up to 16 days.

Dosing will commence on the day prior to RT, continue daily during RT (including days in which RT is not given) and 7 days post RT completion.

Patients will be instructed on the method of administration and provided with an instruction sheet.

The drug can be administered at any time during the day, but the same time should be used each day. Twice daily doses should be administered at approximately 8 to 12hour intervals and for three times daily dosing, first dose to be administered in the morning and two doses administered should be administered at approximately 8-12 hours later. A missed dose should be taken as soon as it is noted as missed. Taking two suppositories at the same time is permitted in order to catch up a missed dose within a day. No more than three suppositories should be taken in a 24-hour period.

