Methodology	
Patients will have a minimum of one (1) lesion which is amenable to radiation therapy and be treated in combination with idronoxil (NOX66).
 
The Study will involve 13-16 days of treatment with NOX66 and radiation therapy as follows:
 
 • Baseline: Tumour assessment scan using CT/MRI, screening laboratory assessments (including PSA levels), and pain assessment (Brief pain Inventory-Short Form) • Day 1-16: NOX66 will be administered rectally (one, two or three suppositories daily, depending on cohort allocation) • Day 2-9: Lesions selected for irradiation will receive palliative dose (20Gy) radiation therapy in 5 fractionated doses over 7 days. • Week 6: Initial follow up scan using CT/MRI, follow up laboratory assessments (including PSA levels), and pain assessment • Week 12: Second follow up scan using CT/MRI, follow up laboratory assessments (including PSA levels), and pain assessment • Week 24: third follow up scan using CT/MRI, follow up laboratory assessments (including PSA levels), and pain assessment • Month 9 (3 months after Week 24): Performance Status (ECOG), scan using CT/MRI/US, PSA measure and pain assessment. • Month 12: Performance Status ECOG), scan using CT/MRI, PSA measure and pain assessment. • Month 15, 18, 21 & 24 (every 3 months after Month 12 follow up visit for another 12 months): Scan using CT/MRI/US & PSA measure. 
Patients will continue to be followed up after 24 months at the discretion of the investigator.
 
The study steering committee (SSC) will review emerging safety data and determine the dose cohort escalation following end of treatment cycle of final patient in a cohort. Following interim analyses of safety data and tumour response at WEEK 6 of 3 dose cohorts of 12 total patients, the SSC will inform on dose for cohort expansion of additional 12 patients.
 
Baseline CT/MRI scans shall be assessed and any lesions which can be measured in accordance with RECIST criteria will be noted as "target lesions". Target measurable lesions may either be at the site of irradiation or non-irradiated. Patients with identified measurable target lesions will be assessed for objective response using RECISTv1.1 criteria. All patients will have radiological scans, PSA, ECOG and pain scores assessed for clinical response by a Radiation Oncology Expert Committee.

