7 STUDY DESIGN

This is an open-label Phase Ib dose confirmation and proof of concept study in up to 24 patients with end stage castrate resistant prostate cancer who are being considered for or undergoing palliative radiation therapy for pain and symptom management. Patients will have a minimum of one (1) lesion which is amenable to radiation therapy. Palliative RT (20Gy over 5 fractions) will be delivered to selected lesion in combination with rectally administered idronoxil (NOX66).

This study is intended to provide information regarding the safety of this treatment combination and justification for a larger Phase 2/3 study in the treatment of patients with combination of NOX66 and palliative radiation therapy.

Clinical response to treatment will be assessed by radiological CT/MRI scans, where applicable objectively measures by RECISTv1.1, by pain response as evaluated by Brief Pain Inventory Short Form, ECOG scores and by monitoring PSA as surrogate marker with overall (observable and symptomatic) response based on data review by an independent Radiation Oncology Expert Committee (ROEC). Local response will be based on investigator review of data in conjunction with ROEC.

PSA will be monitored as a surrogate marker of response and pain response will be evaluated using the Brief Pain Inventory Short Form throughout the study.

Patients will be suitable for the study as they become eligible for, and will be given, palliative radiation therapy for management of their cancer.

Three dose cohorts will be investigated in this study with dosing based on criteria outlined in section 10.2.7. The three doses of idronoxil investigated include:

- 400mg idronoxil provided as one NOX66 suppository per day
- 800mg idronoxil provided as one NOX66 suppository twice daily
- 1200mg idronoxil provided as one NOX66 suppository three times daily.

Treatment will be for one cycle of combined radiation therapy and NOX66 with follow up assessments at Week 6, Week 12, Week 24 and every 3 months for the following 18 months. All patients will be followed up for disease progression and survival information either by retrospective review of medical records or by a physical visit or by telephone follow up call.

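### Section 9.2 leaves the within-day schedule at 1200 mg/day unclear, and its literal reading conflicts with Section 7

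*Combined protocol and SAP*

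**What the plan says.** Section 7 defines the top dose level as "1200mg idronoxil provided as one NOX66 suppository three times daily". Section 9.2 opens in the same terms: the suppository "will be self-administered once, twice or three times daily depending on the patient cohort allocation".

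The detailed timing follows later in Section 9.2. For two doses a day it gives a spacing: "Twice daily doses should be administered at approximately 8 to 12hour intervals". For three doses a day it says: "first dose to be administered in the morning and two doses administered should be administered at approximately 8-12 hours later". No interval is given between the second and third dose, and nothing says whether those two are separate.

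The same paragraph adds a catch-up rule, "Taking two suppositories at the same time is permitted in order to catch up a missed dose within a day", and a daily limit, "No more than three suppositories should be taken in a 24-hour period".

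On quantity, Section 9.1.1 describes "suppositories with an approximate weight of 2.2 g and containing 400 mg drug substance", and the Methodology row of the synopsis gives "one, two or three suppositories daily, depending on cohort allocation". Section 9.1.2 supplies one, two or three boxes of 16 according to cohort.

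**The concern.** The sentence on three-times-daily dosing attaches two doses to a single later time. Followed as written, it gives a different regimen from the one in Section 7: two administrations a day instead of three, the second twice the size of the first. The step from 800 to 1200 mg is then unclear too. It could be an added administration or a doubled second one.

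This matters because the drug is self-administered, and the outcome measures for the primary objective (Section 10.1) include dose-limiting toxicities and the maximum tolerated dose. The top-dose cohort has only 4 patients, and its safety data feed the choice of expansion dose (Sections 10.2.14 and 13.2). If patients in that cohort follow different schedules, a tolerability result labelled 1200 mg mixes regimens. The protocol's own rationale also gives timing some weight: Section 5.2 says the drug needs to be in the tumour cell while damage is induced and repaired, and Section 4.5 reports that in rats it is largely eliminated within 24 hours.

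**Working it through.** **Inputs.** 400 mg per suppository (Section 9.1.1); three per day at the top level (Section 7 and synopsis); at most three in 24 hours (Section 9.2); three boxes of 16 (Section 9.1.2); up to 16 days of dosing (Section 9.2); 4 patients in Cohort 3 and 12 in the expansion (Section 10.2.14).

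**Step 1: the plan's own figure.** 3 × 400 mg = 1200 mg/day, as stated. Supply is 3 × 16 = 48 suppositories, and need is 16 days × 3 = 48. The daily total and the supply agree.

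**Step 2: lay out each reading over repeated 24-hour days.** Let g be the stated 8 to 12 hours and put the morning dose at hour 0.

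- *Reading A, one and then two together.* Doses fall at 0, g and g. The gaps are g and 24 − g, so 8/16 hours at g = 8 and 12/12 hours at g = 12. There are two administrations a day and the largest is 2 × 400 = 800 mg.
- *Reading B, each dose g hours after the one before.* Doses fall at 0, g and 2g. The gap before the next morning's dose is 24 − 2g.
- *Reading C, two separate doses, both inside the window 8 to 12 hours after the morning dose.* For example, doses at 0, 8 and 12 give gaps of 8, 4 and 12 hours. The largest single amount is 400 mg.

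| g (hours) | A: gaps (hours) | A: largest single amount | B: gap before next morning (hours) | B: largest single amount |
|---|---|---|---|---|
| 8 | 8 / 16 | 800 mg | 8 | 400 mg |
| 9 | 9 / 15 | 800 mg | 6 | 400 mg |
| 10 | 10 / 14 | 800 mg | 4 | 400 mg |
| 11 | 11 / 13 | 800 mg | 2 | 400 mg |
| 12 | 12 / 12 | 800 mg | 0 (third dose meets the next morning's first) | 800 mg |

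**Step 3: ask whether any other text settles it.** Every reading totals 1200 mg/day, stays within three suppositories per 24 hours and uses 48 suppositories in 16 days. The cap, the box supply and the synopsis wording therefore cannot separate the readings. Counts of returned suppositories (Sections 9.1.4 and 9.5) cannot either, and Table 1 lists no recording of dose times.

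**Step 4: compare with Section 7.** Reading A does not give one suppository three times a day. Reading C does, and so does Reading B for g below 12 hours. Neither B nor C is spelled out, and they space the doses differently.

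**Step 5: patients concerned.** Cohort 3 receives 1200 mg only if no patient in Cohort 1 or Cohort 2 discontinues for NOX66-related adverse events. The expansion receives it only if the Study Steering Committee then selects it. The ceiling is 4 + 12 = 16 of 24 patients.

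**The case against.** The best reply is that the text, taken as a whole, points to three separate doses. Section 7 and the opening of Section 9.2 both say three times daily. The catch-up rule mentions two suppositories at once only for a missed dose, which implies that separate dosing is the norm. The faulty sentence repeats its verb and looks like an editing slip. This stands in part: the conflict depends on the reading, and a reader who infers a flat contradiction goes too far. It does not remove the problem, because even on the separate-dose readings the spacing is not defined.

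Other stronger inferences are not supported:

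- *That the dose level itself is ambiguous.* It is 1200 mg/day throughout.
- *That three doses cannot fit in a day.* Two intervals of 8 to 12 hours span 2 × 8 = 16 to 2 × 12 = 24 hours, but only if that interval applies between every consecutive pair. Section 9.2 speaks of intervals only for twice-daily dosing.
- *That plasma results would be distorted.* Idronoxil is sampled at baseline, at the end-of-treatment visit (the day after the last dose, Table 1 footnote 3) and at Week 6 (Section 10.4.7). No sample is timed to a peak, so the documents do not show that these data would pick up a 400 versus 800 mg difference.
- *That patients are given this wording.* The instruction sheet is not in the documents and may be clear.

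The protocol also tolerates 800 mg at once as a catch-up, so some variation is accepted. That is an exception for a missed dose and does not define the routine schedule.

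**Conclusion.** The point holds as an unclear schedule at a well-defined daily dose. One stated administration rule, followed literally, gives a regimen that differs from Section 7. Its other readings agree with Section 7 but leave the spacing open. The largest single amount is 400 or 800 mg, a two-fold difference, and the number of administrations is three or two a day.

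The consequence is limited to how uniformly the 1200 mg patients are treated when tolerability and dose-limiting toxicity are read. That concerns 4 patients if Cohort 3 reaches 1200 mg, and at most 16 if that dose is also chosen for the expansion. Whether patients would in fact diverge depends on an instruction sheet that cannot be checked here. Even if the sheet is clear, the governing protocol text gives no single standard for judging adherence or deviations. This review takes no position on which schedule is right.

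**What to change.** The sponsor should reconcile Sections 7 and 9.2 into one statement, for the 1200 mg level, of how many suppositories are taken at each administration and what intervals separate them. The patient instruction sheet should then be checked against that statement. The choice of regimen belongs to the sponsor and investigators. The cost is wording in the protocol and, if needed, in the sheet.

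As an option, administration times could be recorded so that the actual spacing can be reported alongside the toxicity results. This is a new, small data-collection requirement and is not needed for the reconciliation itself.

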9.4 TREATMENT DOSE MODIFICATIONS AND TREATMENT CYCLE DELAY

9.4.1 NOX66

Any patient who experiences toxicity > Grade 2 related to NOX66 will have the idronoxil treatment withheld for 1 day and then resume on the next lower dosage (1200 mg reduced to 800 mg; 800 mg reduced to 400 mg; 400 mg daily reduced to 400 mg every 2nd day) for the remainder of the treatment period.

If toxicity > Grade 2 persists following reduction of dose, the idronoxil treatment will cease immediately for the remainder of the treatment period, although the patient may remain in the study.

There will be no dose modification of NOX66 on the basis of body weight.

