10.2.14 Cohort Allocation and Dose Escalation

[figure not shown]
This study will enrol up to 24 patients across three dose levels of NOX66. Dose cohort assignment will be sequential and dose escalation decisions will be based on patients who experience adverse events directly related to NOX66 treatment and discontinued as described below and outlined in Figure 2.

Dose escalation and decision rules are as follows:

- **Patients 1-4 (Dose Cohort 1)** will be prescribed NOX66 400mg.
- **Patients 5-8 (Dose Cohort 2):** Once fourth patient in Cohort 1 has completed treatment (Visit 7), the dose of NOX66 for next cohort, patients 5-8, will be as determined as follows, based on the number of discontinuations due to NOX66 related adverse events:
 - If no patients discontinue treatment, NOX66 dose will be increased to 800mg
 - If one patient discontinues treatment, NOX66 dose will remain at 400mg
 - If more than one patient discontinues treatment, there will be no further recruitment to the study until scans from WEEK 6 are assessed for disease status
- **Patients 9-12 (Dose Cohort 3):** Once the eighth patient in Cohort 2 has completed treatment (Visit 7), the dose of NOX66 for next cohort, patients 9-12, will be as determined as follows, based on the number of discontinuations due to NOX66 related adverse events:
 - If no patients in Dose Cohort 2 discontinue treatment, NOX66 dose will be increased (from 400mg to 800mg or from 800mg to 1200mg)
 - If one patient in Dose Cohort 2 discontinues treatment, NOX66 dose will remain at the same dose (400mg or 800mg)
 - If more than one patient in Dose Cohort 2 discontinues treatment, dose will be reduced (from 800mg to 400mg) or, if dose has remained at 400mg, there will be no further recruitment to the study until scans at WEEK 6 are assessed for disease status.

Following the review of all accumulated safety data, disease status and treatment efficacy signals from scans assessed per RECIST 1.1 criteria and preliminary pain response at WEEK 6 for all patients, the Study Steering Committee will determine the dose at which to continue treatment for the expansion patient Cohort 4 in the study. A further 12 patients will be recruited at this dose level.

Figure 2: Dose Escalation and Dose Expansion Schema

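### Section 9.2's missed-dose rule carries no cohort qualifier, so one catch-up can put the next dose level's daily amount into 24 hours while that level is still closed

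*Combined protocol and SAP*

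**What the plan says.** Section 9.2 sets the routine frequency by cohort: NOX66 is "self-administered once, twice or three times daily depending on the patient cohort allocation". Three sentences later in the same section name no cohort:

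- The ceiling is a single figure: "No more than three suppositories should be taken in a 24-hour period".
- Doubling up is allowed, subject to an undefined time limit: "Taking two suppositories at the same time is permitted in order to catch up a missed dose within a day".
- The timing of a catch-up is left open: "A missed dose should be taken as soon as it is noted as missed".

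Section 9.1.1 gives the strength: "suppositories with an approximate weight of 2.2 g and containing 400 mg drug substance". Section 7 fixes three daily doses, starting with "400mg idronoxil provided as one NOX66 suppository per day"; the other two are 800 mg as two suppositories and 1200 mg as three.

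Section 10.2.14 opens the levels in sequence. For the second cohort: "If no patients discontinue treatment, NOX66 dose will be increased to 800mg". The same test on Cohort 2 governs the next step. Section 9.4.1 lowers the dose after NOX66-related toxicity above Grade 2: "1200 mg reduced to 800 mg; 800 mg reduced to 400 mg; 400 mg daily reduced to 400 mg every 2nd day".

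No section ties the 24-hour limit or the catch-up permission to the patient's assigned or reduced dose.

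**The concern.** In a sequential escalation, each cohort's tolerability is read as evidence about its assigned dose, and the next level waits for that reading. A dosing instruction that lets a compliant patient take the next level's daily amount within 24 hours does not fit that sequence. It also does not fit Section 9.4.1: a patient just reduced for toxicity can, after one missed dose, take the former daily amount within 24 hours.

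Two things are at stake. One is patient safety during the period when the higher amount has not been reviewed. The other is attribution. Under Section 10.2.14 one NOX66-related discontinuation among four patients holds the dose. More than one pauses recruitment, or in Cohort 2 at 800 mg lowers the dose. The safety analysis in Section 12.2 tabulates events by dose cohort. A discontinuation after a catch-up day is therefore counted against the assigned dose, and nothing described in the protocol would show the committee that more had been taken.

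**Working it through.** **Inputs.** Strength 400 mg (9.1.1). Assigned suppositories per day 1, 2 or 3 (7). At most two at once and at most three in 24 hours (9.2). Twice-daily doses about 8 to 12 hours apart (9.2). Boxes of 16, with 1, 2 or 3 boxes per patient by cohort (9.1.2).

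**Reproducing the plan's figures.** 1 × 400 = 400 mg, 2 × 400 = 800 mg and 3 × 400 = 1200 mg, as in Section 7. Supply is 1 × 16 = 16, 2 × 16 = 32 and 3 × 16 = 48 suppositories, exactly 16 days at 1, 2 or 3 per day.

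**The ceiling against the assigned dose.** 3 × 400 = 1200 mg for everyone: 1200/400 = 3.0, 1200/800 = 1.5, 1200/1200 = 1.0. It holds a patient to the assigned dose only at the top level. The ceiling itself grants nothing. The excess comes from the catch-up sentences, which the ceiling does not stop below 1200 mg.

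**One missed dose, catch-up on the same calendar day only.** A 24-hour period is counted from one dose up to, but not including, the same clock time next day.

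- 400 mg cohort: the 08:00 dose is remembered and taken at 20:00, and the next is taken at 08:00. That is 2 suppositories in 12 hours, (1 + 1) × 400 = 800 mg; 800/400 = 2.0.
- 800 mg cohort, doses at 08:00 and 20:00: the 08:00 dose is missed, two are taken at 20:00 and one at 08:00. That is 3 suppositories in 12 hours, (2 + 1) × 400 = 1200 mg; 1200/800 = 1.5.

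Each calendar-day total stays at the assigned dose.

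**One missed dose, catch-up up to 24 hours late.**

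- 400 mg cohort: yesterday's dose is noticed at today's dosing time and two are taken together, 800 mg on one calendar day.
- 800 mg cohort: last evening's dose is missed, two are taken this morning and one tonight, 1200 mg on one calendar day.

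| Cohort, one missed dose | Most in any 24 hours | Most in a calendar day, same-day catch-up | Most in a calendar day, next-day catch-up |
|---|---|---|---|
| 400 mg | 800 mg | 400 mg | 800 mg |
| 800 mg | 1200 mg | 800 mg | 1200 mg |

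An enumeration of one and two missed doses, with 8-hour and 12-hour spacing for the twice-daily schedule, gave these same one-dose maxima. A 400 mg patient reached 1200 mg in 24 hours only with two missed doses and no limit on how late they could be taken.

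**After a reduction.** The same arithmetic applies. A patient reduced from 1200 to 800 mg can reach (2 + 1) × 400 = 1200 mg, and one reduced from 800 to 400 mg can reach (1 + 1) × 400 = 800 mg, in each case the former daily amount. Supply does not prevent this: boxes are issued by enrolled cohort, dispensed at the enrolment visit and returned at the end-of-treatment visit (9.1.2 and Table 1).

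**Can accountability show it?** Sections 9.1.4 and 9.5 provide for returned medication and inventory counts. A dose missed and later made up leaves the returned count unchanged, so the count cannot reveal the day on which more was taken.

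**The case against.** The strongest reply is that 'within a day' means the same dosing day. The double-up sentence then only lets patients on several daily doses recover their assigned total, and Section 7 defines doses per day, not per rolling 24 hours. On that reading a late dose followed by an on-time one is ordinary dosing variation. This stands in part: calendar-day totals are then never exceeded. But the words are undefined, and Section 9.2 states its own limit per 24-hour period, the unit in which the excess arises on every reading.

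Other replies limit the point:

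- A reader might infer that patients can be treated at a level not yet opened. The documents do not support that. A level is what a cohort is prescribed; a catch-up is brief, follows an omitted dose and adds nothing to the total supplied.
- A reader might take the ceiling to mean three times the dose in the 400 mg cohort. That needs two missed doses and unlimited lateness.
- A reader might suppose that any adverse event moves the escalation. Section 10.2.14 counts discontinuations due to NOX66-related events, and Section 9.4.1 first withholds for a day and reduces.
- Counting such a discontinuation against the lower dose holds or stops escalation, which is the cautious direction, and Section 13.2 sends related events of Grade 2 and above to the committee at once. Both are true, but the dose would still be misattributed, and the protocol does not say that recent intake accompanies those reports.
- Section 5.2 cites 1200 mg in the oral Phase 3 study. Section 4.5 says that NOX66 was made to reduce the metabolism seen with the oral form, and Section 5.3 says that its adverse event profile is not fully established, so the oral experience does not replace the trial's own sequence.
- The patient instruction sheet may be narrower. It is not among the documents, so this cannot be judged.

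**Conclusion.** The point holds as an inconsistency within the protocol. Section 9.2 as written allows, after one missed dose, 2.0 times the assigned daily dose in 24 hours at 400 mg and 1.5 times at 800 mg. Whether the calendar-day total is also exceeded turns on the undefined phrase.

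It concerns escalation patients while the next level is closed (patients 1 to 8 if escalation is uninterrupted, possibly 9 to 12 if a dose is held) and patients reduced under Section 9.4.1. For the latter, the consequence for escalation assumes that stopping NOX66 under 9.4.1 counts as a discontinuation under 10.2.14. How often any of this would happen cannot be estimated without a missed-dose rate. The finding does not show sustained dosing above the assigned level or a breach of the escalation rules.

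**What to change.** The sponsor should reconcile the missed-dose, double-up and 24-hour sentences in Section 9.2 with the daily doses in Section 7, the reductions in 9.4.1 and the sequential opening of levels in 10.2.14. It should also state what 'within a day' means and bring the patient instruction sheet into line. What the clinical rule should be is for the sponsor to decide.

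Days on which a patient took more than the assigned dose should be recorded and shown to the Study Steering Committee at each escalation review. Because accountability gives totals only, this needs a brief dosing record covering the 13 to 16 treatment days.

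The cost is a few sentences in Section 9.2 and the instruction sheet, plus a small added data-collection burden. Sample size and visit schedule are unaffected.
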